3.0 Outcome Measures/Endpoints

3.1 Primary Outcome Measures

The primary outcome measured will be the total average percent of volatile anesthetic (sevoflurane) utilized while subjects are under anesthesia (maintenance phase). The time considered “maintenance phase” under general anesthesia will be measured starting 5 minutes after the induction agents are administered and measurements will stop following

administration of neuromuscular blocker reversal drugs. Data will be collected from computerized anesthetic records.

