3.2 Secondary Outcome Measures

The secondary outcomes measured will be the total dosage of hypnotic agents administered while in the maintenance phase of anesthesia. These agents include: midazolam, lorazepam, diazepam, fentanyl, sufentanil, ketamine, propofol, morphine, and hydromorphone. Additional secondary outcomes measured will include episodes of hypotension (this will be defined as an episode of mean arterial pressure of <65 mmHg), total dosage of vasopressors (such as phenylephrine, ephedrine, vasopressin, or norepinephrine), and the occurrence of EEG isoelectricity, or burst suppression. SedLine images will be recorded for both groups in order to compare rates and duration of burst suppression events. Of note, if the patient has a functioning arterial line in place, we will use measurements from this in preference to a non-invasive blood pressure cuff).

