We will identify subjects who meet inclusion/exclusion criteria on the day of surgery. Following explanation of the study and completion of informed consent, the patient will be randomized into 1 of 2 groups – study group or control group. We plan to use block randomization to keep the groups relatively balanced throughout enrollment. The patient will then be taken to the operating room in normal fashion. Prior to the induction of anesthesia, the Sedline monitor will be placed on the patient's head to ensure the monitor is working properly. For those in the study group, the monitor will be in full view of the anesthesiologist administering the anesthetic. For those in the control group, an apparatus will be placed over the monitor will not be in view of the anesthesiologist. The monitor will still be processing and recording EEGs for both groups. The patient will then be placed under anesthesia and surgery will commence. While under anesthesia, images of the display screen of the Sedline will be collected for later evaluation. Once the surgery is complete, the patient will have the monitor removed and image capture of the display will be stopped prior to exiting the operating room.

Following finalization of the anesthetic record by the staff anesthesiologist, the primary and secondary outcomes will be collected by investigators. The images of the Sedline EEG monitor will also be reviewed by investigators to ensure that appropriate depth of anesthetic was utilized throughout the maintenance phase of anesthesia in the study group. Blinding of the study investigators will not be possible due to the manner in which images of the Sedline readings are collected (it will be readily apparent on the images whether the SedLine data was readily available or concealed from the anesthesia team).

Prior to Enrollment

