7.0 Study Procedures

As noted above, following enrollment on the day of surgery, the Sedline device will be placed on the patient just prior to the induction of anesthesia. Anesthesia

will then be induced, and surgery will proceed as usual. Images will be captured of the display of the Sedline monitor while under anesthesia during the surgical procedure using a recording device. The study group will have the Sedline readings visible to the anesthesiologist in the room and will use the Sedline to guide anesthetic depth. The control group will have the monitor out of view and not visible to the anesthesiologist, but the images of the Sedline monitor will be recorded.

Once the procedure is complete, the Sedline monitor will be removed from the patient and the collection of images will be stopped prior to the patient exiting the operating room.

Following the finalization of the anesthetic records, the desired data will be collected from the anesthetic record. The images of the Sedline readings will also be reviewed by investigators to confirm an appropriate depth of anesthetic was achieved in the study group.

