From a similar study using an outcome (minimum alveolar concentration or MAC) comparable to ours we were able to estimate a coefficient of variation for total average percent of volatile anesthetic to be 0.15.⁴ Working with a feasible sample size of 44 per group and using a power of 90%, 5% significance level, and employing a two-sided test, the study will be able to detect a reduction of 10% in for total average percent of volatile anesthetic between the two groups. Assuming a dropout rate of up to 20%, we will enroll up to 55 patients per group for this study. Here we used a “Tests for the Ratio of Two Means” using sample size software PASS 2019.

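### Randomisation comes before the SedLine is placed and checked, so pre-induction monitor failures and cancelled cases fall after allocation; allocating after the check is a cheap improvement

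*Combined protocol and SAP*

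**What the plan says.** Section 5.0 (Study Design) gives the sequence on the day of surgery. Allocation follows consent directly: "Following explanation of the study and completion of informed consent, the patient will be randomized into 1 of 2 groups". The patient then goes to the operating room, where the device is fitted and tested: "Prior to the induction of anesthesia, the Sedline monitor will be placed on the patient's head to ensure the monitor is working properly". Section 7.0 agrees that fitting comes just before induction, after enrolment.

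Both arms wear the device: "The monitor will still be processing and recording EEGs for both groups". Only visibility of the display differs. In the study arm the anesthesiologist "will use the Sedline to guide anesthetic depth"; in the control arm the display is hidden.

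The primary outcome is average sevoflurane percent during maintenance, and Section 3.1 gives its source: "Data will be collected from computerized anesthetic records". The outcome that needs the device is burst suppression (Section 3.2): "SedLine images will be recorded for both groups in order to compare rates and duration of burst suppression events".

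Section 12.0 sizes the trial on 44 evaluable patients per group and then adds an allowance: "Assuming a dropout rate of up to 20%, we will enroll up to 55 patients per group". It gives no cause for the dropout, defines no analysis set, and does not say what happens to a patient whose monitor fails. Section 11.0 covers only withdrawal at the patient's wish. Section 4.2 excludes surgery that prevents lead placement, but has no criterion for a poor signal or a device fault.

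**The concern.** The check is described as being there "to ensure the monitor is working properly", but it happens too late to keep anyone out of the randomised set. Two kinds of event can fall between allocation and induction.

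- **The monitor fails the check.** In the control arm the patient still receives the assigned care, and only the image-based outcome is lost. In the study arm the assigned guidance cannot be delivered. The primary outcome is still recorded, but with no contrast to measure in that patient.
- **The case is cancelled.** The primary outcome is lost in whichever arm the patient was assigned to, and an allocation is used up.

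At stake are dilution of the treatment effect in an as-assigned analysis and a few wasted allocations. There is also a conditional risk. Because the plan does not say how failed-monitor patients are handled, they could later be left out of the study arm alone, and that comparison would no longer be protected by randomisation.

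**Working it through.** **Inputs (Section 12.0).** Coefficient of variation 0.15; reduction to detect 10%, i.e. ratio of means 0.90; two-sided 5% level; power 90%; 44 evaluable and 55 enrolled per group; sizing by a test for the ratio of two means.

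**1. Reproduce the plan's figure.** On the log scale:
- σ = √ln(1 + 0.15²) = 0.1492
- δ = |ln 0.90| = 0.1054
- The normal approximation gives 43 per group. With the noncentral t distribution, power is 89.9% at 43 and 90.6% at 44, so 44 is the smallest size that reaches 90%.
- 44 / (1 − 0.20) = 55.

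The stated 44 and 55 are reproduced. Moving the point of randomisation does not change them.

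**2. Simple loss of patients.** If the full allowance is lost in both arms, 44 v 44 remain and power is 90.6%, as planned. If it is lost in the study arm only, 44 v 55 remain and power is 93.3%. With no loss, 55 v 55 gives 95.6%. Loss within the allowance does not bring power below 90%.

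**3. Dilution, with failures kept as assigned.** Let f be the share of study-arm patients whose monitor fails, and assume that they show no effect. The mean difference becomes δ(1 − f), and the noncentrality is δ(1 − f) / (σ√(2/n)). The documents give no value for f, so the rates below are assumptions.

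| f (assumed) | δ(1 − f) | Power, 55 per arm | Power, 44 per arm |
|---|---|---|---|
| 0 | 0.1054 | 95.6% | 90.6% |
| 2% | 0.1033 | 94.9% | 89.4% |
| 5% | 0.1001 | 93.7% | 87.5% |
| 10% | 0.0948 | 91.1% | 83.8% |
| 20% | 0.0843 | 83.6% | 74.6% |

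The 44-per-arm column is the case in which the whole 20% allowance is used up for other reasons and failures occur among those who remain. Because 44 gives only 90.6%, even 2% failure takes it just under 90%. σ is held fixed throughout. Mixing patients with and without effect would raise it slightly: at f = 20% the added study-arm variance is 0.2 × 0.8 × 0.1054² = 0.0018, against σ² = 0.0223.

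**4. Bias, only if failures are dropped from the study arm.** Suppose the dropped patients need k SD more sevoflurane than those kept. The study-arm mean then falls by f·k·σ on the log scale with no true effect. Both f and k are assumptions.

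| f | k | Spurious reduction | Type I error |
|---|---|---|---|
| 5% | 0.5 | 0.4% | 5.2% |
| 10% | 0.5 | 0.7% | 5.7% |
| 20% | 0.5 | 1.5% | 7.8% |
| 20% | 1.0 | 2.9% | 16.5% |

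These figures compare with a 10% target. They describe an exclusion that the documents do not plan.

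**The case against.** The strongest reply is that the order by itself loses nobody on the primary outcome. Sevoflurane percent is read from the anesthetic record in both arms, and no section withdraws, replaces or excludes a patient whose monitor fails. Failure in the study arm is non-delivery of guidance, not dropout. That is correct, and it limits the point to dilution and to cases cancelled before induction.

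It also disposes of several stronger readings that a reader might infer:

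- **That losses are greater in the study arm.** The documents do not show this. The device is fitted and recorded in both arms, so failure removes the burst-suppression data in either. Nothing suggests that cancellation differs by arm. Section 5.0 describes a review of images for appropriate depth in the study group only, by investigators who cannot be blinded, but attaches no exclusion to it.
- **That an as-assigned analysis would be biased.** It would be diluted. Bias needs selective exclusion from one arm.
- **That the 20% allowance reflects monitor failures, or that power falls short.** Section 12.0 gives the allowance no cause, and using all of it leaves the planned power.
- **That early allocation alters care before induction.** No section says when the anesthesiologist learns the arm. Section 5.0 discourages midazolam, and measurement starts five minutes after the induction agents (Section 3.1). With later allocation the arm would still be known before induction.

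It can also be said that the remedy is partial, since it does not stop signal loss during surgery, and that naming an as-assigned analysis set would settle the handling question without moving randomisation. Both are true. Neither removes the sequencing point: naming the analysis set does not avoid the dilution, whereas checking first avoids the pre-induction part of it.

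**Conclusion.** The point holds as a cheap improvement, not as a flaw that threatens the trial. Randomisation precedes monitor placement and the function check, and only the study arm needs a working monitor to receive its assigned care.

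The size depends on a failure rate that the documents do not give. If all 55 per arm are analysed and failures show no effect, power stays above 90% at 5% and 10% failure and falls to 83.6% at 20%. With 44 per arm it falls below 90% at each of these rates, to 74.6% at 20%. These results rest on the plan's coefficient of variation of 0.15 and 10% reduction, and on every failure being kept with no effect. They count all failures, whereas the proposed change avoids only those found before induction, so its gain in power is smaller than the full drop shown. The sample size is unaffected.

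**What to change.** In Section 5.0, with matching edits in Sections 6.0 and 7.0, open the concealed allocation in the operating room once the leads are on and the signal check has succeeded, immediately before induction. Then cover the display or leave it visible according to arm. Patients who fail the check, or whose case is cancelled before it, are not randomised.

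In Section 12.0, state that all randomised patients are analysed as assigned for the primary outcome, including those whose signal fails during surgery, and that monitor failures are reported by arm. Make clear that the 110 subjects in Sections 6.0, 8.0 and 15.0 are randomised patients.

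The cost is small. The device is already fitted in both arms before induction and covered in one, so the new requirement is a concealed allocation that can be opened in the operating room. A few consented patients will not be randomised, so somewhat more than 110 may need to be approached. Failures during surgery are not prevented; the as-assigned rule covers those.

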1.0 Background & Rationale

Electroencephalography (EEG) was first described in 1875 in dogs and apes.¹ The technology was shortly after applied to humans and within 10 years the changes to the EEG tracing was studied when certain sedatives drugs were administered.¹ Over the last several decades EEG based monitors have been developed with the hopes of aiding anesthesiologists at evaluating the “depth” of a patient’s anesthetic while under general anesthesia. Currently, typical anesthesia practice is to measure and adjust depth of a general anesthetic based on the medications administered and hemodynamic parameters of the patient, potentially exposing high risk patients to un-needed excessive depths of anesthesia which can potentially result in adverse post-operative outcomes.^{2,3}

The use of intraoperative EEG monitoring to guide the depth of an anesthetic seems to have the potential to reduce the total dose of anesthetic required. Use of the EEG based monitor called the Bispectral Index Monitor (BIS Monitor) in an older study was shown to reduce sedative use and total cost in ICU patients who were receiving intravenous infusions of sedatives and neuromuscular blockers.⁴ And recently, the BIS monitor was used in a large randomized control study in order to investigate whether providing an anesthetic guided by an EEG based monitoring device in individuals at high risk for postoperative delirium would significantly reduce postoperative delirium. While the primary results reported a negative results, the study did have other interesting findings – most notably a significant reduction in the dosage of volatile anesthetic (the primary anesthetic agent used in general anesthetic procedures). Furthermore, the study showed using a protocolized adjustment in anesthetic depth using an EEG based monitoring system for guidance in human subjects resulted in no significant change in adverse outcomes in a large trial of patients in this population⁵

The Masimo Sedline Brain Function Monitor (SedLine), is an EEG based monitoring device that is approved by the Food and Drug Administration for monitoring of brain function under anesthesia. This new generation device provides processed EEG information (as the BIS monitor does) as well as raw EEG waveforms and a Density Spectral Array (DSA) display – providing information of the power of the EEG signal over a spectrum of frequencies. This additional

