5.0 Study Design

[figure not shown]
- Prior to study commencement, select anesthesiologists from the Indiana University Health University Hospital Anesthesia Group will be trained on usage and interpretation of the Sedline. Training for this group of providers will include a PowerPoint presentation recording presented by [name] to aid in interpretation of the Sedline data. Representatives from the study will also be available as needed to answer questions as they arise. They will also be given certain guidelines for anesthetic administration based on the processed EEG findings. These will include the following:
 - Usage of sevoflurane as the primary anesthetic agent
 - Reducing sevoflurane dosage if the EEG indicates signs of burst suppression (excessive anesthetic depth), if the PSI on the Sedline reads less than 25, or if hypotension is occurring and the anesthesia provider believes that depth of anesthesia may be a contributing factor.
 - Increasing sevoflurane dosage if the EEG pattern is not consistent with general anesthesia (not enough depth of anesthetic).
- We anticipate 5-10 anesthesiologists being included in this group. Given that this group of anesthesiologists will be assigned to both groups (study and control), the size of the groups, and the instructions regarding the maintenance phase of anesthesia, diazepam, and dexmedetomidine we anticipate the difference in practice patterns between providers will not affect the data. We will discourage the use of nitrous oxide as well as IV anesthetics including midazolam. In the control group, the anesthesiologist will be asked to provide the anesthetic as he or she would under normal care with the exception of avoidance of nitrous oxide and IV anesthetics during the maintenance phase of anesthesia. We anticipate

that the surgical procedures included in this study will be similar enough that the type of surgical procedure will not affect anesthetic dosing.

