6.0 Enrollment/Randomization

The surgical schedule will be assessed daily to identify patients scheduled for surgery who may be eligible to participate in this study. A member of the research team, either principal investigator, co-investigator, or study coordinator will approach the potential subject the day of their scheduled procedure. They will conduct the visit in a private area such as a patient's room, secluded hospital room, or an area free from the general public. All study procedures will be reviewed, questions answered, and the subject will be given ample time to discuss and determine if they will sign the consent to participate in the study.

We plan to enroll 110 subjects in this study. Patients will be randomized to either the control or the study group.

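### Burst suppression, one secondary outcome, is compared between arms from screen images that reveal the arm, and no masking before scoring is planned

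*Combined protocol and SAP*

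**What the plan says.** Section 3.2 makes isoelectricity or burst suppression a secondary outcome and names its source: "SedLine images will be recorded for both groups in order to compare rates and duration of burst suppression events". Section 12.0 lists burst suppression episodes again among the secondary outcomes but names no test for them.

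Section 7.0 describes the capture: "Images will be captured of the display of the Sedline monitor while under anesthesia during the surgical procedure using a recording device". In the control group the monitor is covered; in the study group it is in full view (section 5.0). The images are collected for later evaluation (section 5.0) and stored on a research computer (section 10.0).

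Section 5.0 says that "the primary and secondary outcomes will be collected by investigators". It then says "Blinding of the study investigators will not be possible due to the manner in which images of the Sedline readings are collected", and explains that "it will be readily apparent on the images whether the SedLine data was readily available or concealed from the anesthesia team". No other reason is given. Section 13.0 limits quality control to range checks, database testing, single entry with random accuracy checks, and periodic extraction and cleaning.

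The primary outcome, average sevoflurane percent during maintenance, is taken from computerized anesthetic records (section 3.1).

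**The concern.** The anesthesiologist has to know the arm in this design. The person who later reads stored images may not have to. Section 5.0 explains why the images, as captured, show the arm. It does not explain why they must be scored in that state.

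If the reader knows the arm, reading errors may differ between arms. An apparent difference in burst suppression could then partly reflect the reader, or a real difference could be hidden. Masking does not remove reading error. It makes the error more likely to be the same in both arms, and error of that kind does not inflate the false-positive rate.

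At stake is one secondary comparison. It has some interest of its own, because signs of burst suppression are one of the cues in the dosing guidance of section 5.0, so the outcome bears on whether guidance worked.

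**Working it through.** **Reading the sections together.** Section 3.2 (images are the source, arms are compared), section 5.0 (investigators collect the outcomes, the arm is apparent on the images) and section 13.0 (no masked or duplicate reading) lead to one conclusion: as written, burst suppression can be scored by someone who sees the arm. No single sentence names the scorer; this follows from sections 3.2 and 5.0 together.

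**The plan's own figure.** The illustration uses 44 per group from section 12.0, so that was checked first. For a ratio of means of 0.90 and a coefficient of variation of 0.15, the log-scale difference is |ln 0.90| = 0.105 and the SD is √ln(1 + 0.15²) = 0.149. A two-sided 5% t-test first reaches 90% power at 44 per group (90.6%). Then 44/(1 − 0.20) = 55 per group, 110 in total. The figures reproduce, and the present point changes none of them.

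**Illustration of size.** The documents give no burst suppression rate and no reading error rate, so every rate below is assumed. The endpoint is per-patient occurrence only, not rates or duration. There are 44 patients per group, the test is two-sided at 5%, and probabilities come from full enumeration of the two binomials. Fisher's test and Pearson's chi-square (no continuity correction) are both shown, because section 12.0 names these two for hypotension and none for burst suppression.

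*False positives, no true difference.* The true rate is p in both arms. If a share u of true cases is missed in the study arm only, the observed rates are p and p(1 − u). For example, p = 0.60 and u = 0.10 gives 0.60 against 0.54.

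| Error | Test | p = 20% | p = 40% | p = 60% |
|---|---|---|---|---|
| None | Fisher | 2.5% | 2.9% | 2.9% |
| None | Pearson | 5.4% | 5.2% | 5.2% |
| 10% missed, study arm | Fisher | 2.9% | 4.3% | 5.3% |
| 10% missed, study arm | Pearson | 6.0% | 7.2% | 8.6% |
| 20% missed, study arm | Fisher | 4.2% | 8.5% | 13.6% |
| 20% missed, study arm | Pearson | 8.2% | 13.0% | 19.3% |
| 20% missed, both arms | Fisher | 2.5% | 3.0% | 2.6% |

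The last row is the situation that masking aims for: the same error, shared equally, leaves the rate where it was.

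*Power, true rates 50% (control) and 25% (study), Fisher.* If a share v of true negatives is over-called, the observed rate is p + v(1 − p).

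| Over-calling | Observed, control / study | Power |
|---|---|---|
| None | 0.500 / 0.250 | 61% |
| 5%, study arm only | 0.500 / 0.2875 | 45% |
| 5%, both arms | 0.525 / 0.2875 | 54% |
| 13%, study arm only | 0.500 / 0.3475 | 22% |
| 13%, both arms | 0.565 / 0.3475 | 43% |

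Moving from one-arm to shared error regains 54 − 45 = 9 of the 61 − 45 = 16 points lost in the 5% case, and 43 − 22 = 21 of the 61 − 22 = 39 points lost in the 13% case. The rest is the cost of reading error as such, which masking leaves in place.

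**The case against.** The strongest reply is that the plan is open about the limitation, that it touches one of several secondary outcomes, and that nothing shows the bias to be large. The monitor "provides processed EEG information (as the BIS monitor does) as well as raw EEG waveforms". The documents do not say which of these is scored. If a displayed value is simply transcribed, there may be little room for judgement. All of this stands, and it is why the point is rated as optional.

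A second reply is that masking may not work. The readable text does not describe the cover or the recording set-up, and a figure in section 5.0 is not available to us. Cues may lie within the display area, or the trace itself may suggest guided care. This also stands: the documents neither show that cropping would hide the arm nor say that it was considered.

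Some stronger readings are not supported:

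- A reader might infer that the scorer knows the arm from other roles, since "either principal investigator, co-investigator, or study coordinator will approach the potential subject" and "Representatives from the study will also be available as needed to answer questions as they arise". But section 5.0 places randomization after consent, so approaching a patient does not reveal the arm. The second sentence sits in the text on training and need not mean support during a case.
- A reader might infer that the sevoflurane result is compromised. It is taken from computerized records, not from images.
- A reader might take the power figures as the gain from masking. The shared-error rows show that only part of the loss is regained.

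A more lenient reading also fails, namely that small errors keep the false-positive rate under 5%. With 10% missed it reaches 5.3% with Fisher and 6.0% to 8.6% with Pearson.

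**Conclusion.** The point holds in a limited form. The plan compares burst suppression between arms from images that show the arm, gives only the manner of collection as the reason for not blinding, and includes no masking step before scoring. This leaves the comparison open to reading error that differs between arms.

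The direction and size of any bias are unknown. The illustration shows that bias is possible and roughly how it would scale under assumed error and event rates; it does not show that bias is likely here, and it does not cover rates or duration. The primary conclusion is unaffected. Severity: optional improvement to a secondary outcome.

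**What to change.** In section 5.0, limit the statement that blinding is not possible to the other outcomes and the depth review, and add:

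> *For burst suppression, images will be cropped or masked to the display area where feasible and given a random case code by one existing team member, and scored under that code, with arms mixed, by another existing team member before the arm is revealed. Where an image still reveals the arm, this will be recorded and the result reported as not fully blinded.*

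The cost is a few protocol sentences and preparation time for up to 110 cases. Two existing team members must share the work, which may be tight because team size is not stated. Patient care does not change. Masking may be incomplete, which is why the last sentence of the insertion is needed.

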13.0 Statistical Data Management

Primary data will be collected via review of electronic medical records, anesthesia records, and screenshot images of the SedLine EEG monitor and will be stored electronically in REDCap. The storage location will be backed up automatically. Quality assurance steps will include, built-in range checks and testing of the database by the study team prior to moving to production mode. The following quality control methods will be used: 1) single data entry with random checks of accuracy; and 2) extraction and cleaning of data that will be used for analysis every 6 months.

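### The reason given for unblinded outcome collection applies to the SedLine images but not to sevoflurane percent, and the plan does not mask collection, averaging or cleaning of the primary outcome

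*Combined protocol and SAP*

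**What the plan says.** All references are to the combined protocol and SAP.

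- **Source of the primary outcome.** Section 3.1 defines it as the average sevoflurane percent over the maintenance phase and adds: "Data will be collected from computerized anesthetic records". Section 7.0 repeats that "the desired data will be collected from the anesthetic record", and treats review of the SedLine images as a separate activity.
- **Window.** Section 3.1 says the maintenance phase "will be measured starting 5 minutes after the induction agents are administered and measurements will stop following" the reversal of neuromuscular blockade.
- **Who collects.** Section 5.0 says that, once the record is final, "the primary and secondary outcomes will be collected by investigators".
- **Blinding.** The same paragraph says "Blinding of the study investigators will not be possible due to the manner in which images of the Sedline readings are collected", with one reason: "it will be readily apparent on the images whether the SedLine data was readily available or concealed from the anesthesia team".
- **Use of the images.** They serve the burst suppression comparison (section 3.2) and the review of anesthetic depth in the study group (sections 5.0 and 7.0).
- **Data handling.** Section 13.0 describes record review, storage in REDCap, range checks, database testing, "single data entry with random checks of accuracy", and extraction and cleaning every 6 months. It does not say who enters or cleans the data, or whether the arm is visible to them.

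**The concern.** The stated obstacle to blinding lies in the images, and the primary outcome does not come from the images. The plan nevertheless gives both tasks to the same group and offers no masking for either.

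Sevoflurane percent is recorded by machine, but the endpoint is a derived average. Someone has to place the start and end of the window and turn a series of readings into one number. Section 3.1 gives no reading interval or time weighting, and does not say which dose counts if induction or reversal drugs are given more than once. Choices left open in this way could lean towards the hypothesis, stated in section 1.0, that monitoring lowers the dose. Random accuracy checks look for entry errors. They are not designed to find a small tendency that runs with the arm.

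At stake is the one endpoint on which the trial is powered. A systematic shift between arms would add directly to the estimated difference and raise the false-positive rate.

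**Working it through.** **1. The passages side by side**

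| Item | Source in the plan | Does the image reason apply? |
|---|---|---|
| Sevoflurane percent (primary) | Computerized anesthetic record (3.1, 7.0) | No |
| Blood pressure, hypnotic and vasopressor doses | Anesthetic record (5.0, 7.0) | No |
| Burst suppression | SedLine images (3.2) | Yes |
| Review of anesthetic depth | SedLine images (5.0, 7.0) | Yes |

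The reason covers one secondary outcome and one quality review. No section provides a masked collector for the rest, or requires sevoflurane to be collected before the images are seen.

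**2. The plan's own sample size**

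Inputs from section 12.0: CV 0.15, 10% reduction, two-sided 5% level, 90% power, 44 per group, 20% dropout, ratio of two means.

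- Log-scale SD: sqrt(ln(1 + 0.15²)) = sqrt(ln 1.0225) = 0.1492.
- Log-scale effect: |ln 0.90| = 0.1054.
- Power by noncentral t: 0.899 at 43 per group and 0.906 at 44, so 44 is the smallest size that reaches 90%.
- Dropout: 44 / 0.80 = 55 per group, 110 in total.

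The stated figures reproduce, and nothing below changes them.

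**3. Sensitivity of the test to an arm-related shift**

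- Standard error of the log ratio: 0.1492 × sqrt(2/44) = 0.0318.
- With no true effect and a net shift of b in one arm's mean, the test statistic has noncentrality |ln(1 − b)| / 0.0318 on 86 degrees of freedom. The rejection probability is the noncentral t area beyond both 5% critical values.

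| Assumed net shift b | Noncentrality | Two-sided error rate |
|---|---|---|
| 0.5% | 0.158 | 5.3% |
| 1% | 0.316 | 6.1% |
| 2% | 0.635 | 9.6% |
| 3% | 0.958 | 15.7% |

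The values of b are assumptions. The documents give no size for abstraction error, in total or by arm.

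**4. How much window error a given shift needs**

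Assume 180 minutes of maintenance, and readings in the wrongly assigned minutes that differ from the patient's mean by half of it. Neither figure is in the documents.

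- A 1-minute error in every patient of one arm: 0.5 × 1/180 = 0.28%, error rate about 5.1%.
- A 5-minute error in every patient of one arm: 0.5 × 5/180 = 1.4%, error rate about 7.2%.

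Under these assumptions, a shift of 2% or 3% from window setting alone would need errors that are longer still and consistent across one arm.

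**The case against.** The strongest reply is that a recorded gas concentration leaves little room for judgement. Section 3.1 ties the window to drug-administration events, random transcription error adds noise and not bias, and step 4 shows that small boundary errors hardly move the error rate. Much of the remaining discretion would also disappear if the averaging rule were simply written down, whoever applied it. All of this stands, and it is why the point has low priority.

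A reader might infer more than the documents support:

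- **That the blinding sentence is false.** It follows directly on the image review, and its parenthesis concerns only the images. It is true of anyone who has viewed them. The fault is that the plan does not separate that task from collection of sevoflurane.
- **That investigators who know the arm enter and clean the data.** Section 5.0 assigns outcome collection to investigators, but section 13.0 names nobody for entry, extraction or cleaning and is silent on whether the arm is visible.
- **That random checks are the only control.** Section 13.0 also lists range checks and database testing. None of these is said to be masked, but they are there.
- **That the data can certainly be exported by script.** The records are computerized. No section describes a time-stamped export or access to one.
- **That the error rate is inflated.** The calculation shows how sensitive the test is to an assumed shift. It is not evidence that a shift will occur.

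**Conclusion.** The point holds in a limited form. The reason given for unblinded collection does not extend to sevoflurane percent, blood pressure or drug doses, and no part of the plan masks the setting of the window, the averaging or the cleaning. Those steps may therefore be carried out with knowledge of the arm.

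The size of any resulting bias is unknown. Under the section 12.0 assumptions, a net between-arm shift of 0.5% would leave the error rate at about 5.3%, while 1% to 3% would take it from about 6.1% to 15.7%. Shifts at the upper end would need sizeable and consistent misabstraction in one arm, and nothing in the documents suggests this.

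The sample size is unaffected. The case for a change is that it costs little and protects the powered endpoint.

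**What to change.** Make the following changes in sections 3.1, 5.0 and 13.0:

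1. In 5.0, limit the statement that blinding is not possible to review of the SedLine images and the outcome read from them.
2. In 3.1 and 13.0, state that sevoflurane values and the event times that define the window are taken from the anesthetic record keyed to study number without the arm code, by electronic export where the record system allows, and before that patient's SedLine images are reviewed.
3. In 3.1, fix one averaging rule or script before the first extraction. It should cover time weighting, gaps in the readings, and which administration sets each end of the window.
4. In 13.0, run the 6-monthly cleaning on pooled data without the arm code.

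The cost is a short programming and data-handling effort plus wording changes. If export is not available, items 1, 3 and 4 and the order of work in item 2 can still be adopted.

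The change does not remove the treating anesthesiologist's knowledge of the arm, which is part of the intervention. Nor does it mask a team member who learned the allocation at enrollment, although a fixed rule leaves such a person little to decide.
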